4 SUBJECT ELIGIBILITY

4.1 INCLUSION CRITERIA

A subject is eligible to participate in this study if all of the following criteria apply:

1. The subject voluntarily provides informed consent to participate in the study.
2. The subject participated in Study TDE-PH-310 and met the definition of clinical worsening (as specified in Protocol TDE-PH-310), remained on study drug, was compliant with study procedures and assessments during the TDE-PH-310 Study or was currently enrolled in that study at the time the study was discontinued by the Sponsor.
3. All WOCBP must practice true abstinence from intercourse when it is in line with their preferred and usual lifestyle, or use 2 different forms of highly effective contraception for the duration of the study, and for at least 30 days after discontinuing study medication. Medically acceptable forms of effective contraception include: (1) approved hormonal contraceptives (such as birth control pills), (2) barrier methods (such as a condom or diaphragm) used with a spermicide, (3) an intrauterine device, or (4) partner vasectomy. For women of childbearing potential, a negative urine pregnancy test is required at Baseline (study entry) prior to initiating study medication. WOCBP includes any female who has experienced menarche and who has not undergone successful surgical sterilization (hysterectomy, bilateral tubal ligation, or bilateral oophorectomy) or is not postmenopausal (defined as amenorrhea for at least 12 consecutive months).
4. Males participating in the study must use a condom during the length of the study, and for at least 48 hours after their last dose of study medication.

4.2 EXCLUSION CRITERIA

A subject is not eligible to participate in this study if any of the following criteria apply:

1. The subject is pregnant or lactating.
2. The subject has received infused or inhaled prostacyclin therapy for 29 days or more.
3. The subject was prematurely discontinued from Study TDE-PH-310 for reasons other than a clinical worsening event.
4. The subject developed a concurrent illness or condition during the conduct of TDE-PH-310 which, in the opinion of the Investigator, would represent a risk to overall health if they enrolled in this study.

4.3 PRESCRIBED THERAPY

4.3.1 Concomitant Medications

In this open-label study, there are no restrictions on concomitant medications, including the approved PAH therapies, with the exception of the permanent addition (29 days or more) of prostacyclin or prostacyclin analogue therapy. Subjects who receive permanent prostacyclin or prostacyclin analogue therapy must discontinue this open-label study.

5 SUBJECT ENROLLMENT

5.1 TREATMENT ASSIGNMENT

All subjects will receive UT-15C SR tablets during this open-label study. Subjects will retain the same subject number as assigned for the TDE-PH-310 study.

5.2 RANDOMIZATION

This study is not randomized.

5.3 BLINDING

This study is not blinded.

6 DRUGS AND DOSING (OR TREATMENT PROCEDURES)

6.1 DRUG DOSAGE, ADMINISTRATION AND SCHEDULE

The UT-15C tablets are sustained release osmotic tablets. UT-15C tablets are provided as 0.125, 0.25, 0.5, 1.0, and 2.5 mg tablet strengths. The 0.125, 0.25, 0.5, 1.0, and 2.5 mg tablets are colored blue, green, white, yellow, and pink, respectively. The formulation contains pharmaceutically acceptable excipients used in other approved drug products.

For subjects who were randomly allocated to receive placebo in TDE-PH-310, dosing of UT-15C will be initiated and optimized as in the previous protocol, including all safety monitoring and periodic telephone contacts. That is, the first dose of UT-15C (0.125 mg) should be taken by the subject at the site immediately after (approximately 10 minutes) consuming food. Oral dosing of study drug will be continued at 0.125 mg TID (every 6 to 8 hours) immediately after (approximately 10 minutes) consuming food. Subjects must be instructed to take the appropriate amount of UT-15C tablets based upon their prescribed dose. For the first 4 weeks, each dose of study drug should be adjusted in 0.125 mg increments no

more than every 24 hours as clinically indicated. Following 4 weeks of treatment, each dose of study drug may be adjusted in 0.125 or 0.25 mg increments every 24 hours as clinically indicated. Doses of UT-15C should continue to be increased in the absence of dose-limiting drug-related adverse effects, to ensure the subject receives the optimal clinical dose throughout the study. There is no maximum dose of UT-15C in this open-label study.

Subjects who were randomly allocated to receive UT-15C in TDE-PH-310 will begin the open-label study at the same dose they were receiving at the Study Termination Visit in TDE-PH-310, and subsequent adjustments will be made based on symptoms of PAH and adverse effects.

All subjects must be instructed to take the appropriate amount of 0.125, 0.25, 0.5, 1.0 and/or 2.5 mg tablets based upon their prescribed dose. All dose changes should be conducted under appropriate medical supervision in consultation with the study site. At least weekly telephone calls between site personnel and the subject should be made during the first 12 weeks of the study to monitor AEs and make decisions about dose titration. After Week 12, at least monthly telephone calls should be made to continue to monitor AEs and make decisions regarding appropriate dose titrations. If dose titration is considered appropriate, site personnel will instruct the subject to modify their dose and the dose change will be recorded in source documentation. If it becomes necessary for a subject to modify their dose of UT-15C (eg, due to an AE) without prior instructions from site personnel, the subject should be instructed to contact the site as soon as possible and report any dose changes to site personnel for updating in source documentation.

In the event of continued intolerable AEs, dose reductions may occur. The exact dose reduction and frequency of dose reduction should be based on the clinical condition of the subject and the severity/seriousness of the event. In general, dose reductions may occur in 0.125 or 0.25 mg increments every 12 to 24 hours. Larger dose reductions may be necessary in the event of an emergency situation.

6.2 ACCESS TO BLINDED TREATMENT ASSIGNMENT

This study is not blinded.

6.3 COMPLIANCE

The Principal Investigator or other site personnel under the direction of the Principal Investigator will be responsible for dose titration of UT-15C and recording all dosing information in source documents. During telephone calls, site personnel will record the current dosing regimen of UT-15C and determine if the subject is taking UT-15C as prescribed.

At scheduled study visits, subjects should be instructed to bring all study drug (including empty and unused bottles) to the investigational site. Upon return of study drug at each required protocol visits (eg, Weeks 6, 12, 24, etc), the study coordinator or pharmacist must document the number of returned tablets of each strength and determine if the appropriate amount of study drug remains based upon the dose of study drug prescribed. Each subject will also be asked at each visit whether he or she has been compliant with dosing instructions. Subject compliance with the prescribed dosage regimen will be monitored throughout the study. If it is determined that a subject is not compliant with study drug, then site personnel must re-educate the subject on proper dosing compliance and its importance. Continued noncompliance may lead to withdrawal of the subject from the study, after consultation between the Investigator and the Sponsor.

Upon return of study drug at all protocol-required on-site study visits (eg, Weeks 6, 12, 24, etc), all bottles of study drug will be collected. Study drug returned will not be re-dispensed to the subject. Site personnel will dispense a new supply of study drug at each protocol-required visit for the subsequent interval. If necessary, additional study drug may be dispensed in between protocol-required visits at unscheduled visits.

7 EXPERIMENTAL PROCEDURES

7.1 TREATMENT PHASE

7.1.1 *Baseline/Study Entry*

All data collected at the subject's Study Termination Visit during TDE-PH-310 and prior to initiating open-label study drug will serve as Baseline/Study Entry assessments for this study. Following completion of the Study Termination assessments for a subject and entry of required data into the interactive voice or web response system (IVRS/IWRS), the site

personnel will be unblinded to that subject's treatment assignment. Subjects must sign an ICF and meet inclusion/exclusion criteria specific to this protocol. The recommended sequence of events for Baseline/Study Entry is displayed below:

- Informed consent (prior to any study assessments)
 - Inclusion/exclusion criteria
 - Vital signs (following at least 5 minutes of rest)*
 - Physical examination*
 - WHO Functional Class*
 - AE assessment*
 - 6MWT/Borg dyspnea score (for subjects randomized to UT-15C in TDE-PH-310, the 6MWT to be initiated 3 to 6 hours after the last dose of UT-15C; 6MWT to be conducted following at least 5 minutes of rest; Borg dyspnea score to be conducted immediately following 6MWT)*
 - Urine pregnancy test (for WOCBP)*
 - Clinical laboratory assessments*
 - Plasma NT-proBNP*
 - Study drug dosing (for subjects randomized to placebo in TDE-PH-310, the initial dose of UT-15C in TDE-PH-311 should be taken at the study site)
 - Drug accountability
 - Concomitant medications*
 - Weekly telephone calls are highly recommended especially after any dose changes
- *assessments conducted during the Study Termination Visit for the TDE-PH-310 study will not need to be repeated*

The AEs that were ongoing at the end of the TDE-PH-310 study will be recorded as ongoing events for this open-label study. Concomitant medications that were ongoing at the TDE-PH-310 Study Termination Visit will be recorded in the eCRF for the open-label study. Once the subject signs the ICF for this study, all ongoing AEs must be recorded and documented on the eCRF. All AEs and concomitant medications will be reported continuously for the duration of the study. Phone calls to the subject must begin within 1 week of the subject receiving the first dose of study drug and continue to be made weekly for the first 12 weeks of the study. After the first 12 weeks, phone calls must be made at least monthly. Dose titration should occur as needed in accordance with Section 6.1.

7.1.2 Week 6 Visit

Subjects are to return to the study site at Week 6. This visit should be conducted within 14 days of the scheduled visit (as determined by the Baseline/Study Entry Visit) and the following assessments are to occur in the order recommended below:

- Vital signs (following at least 5 minutes of rest)
- WHO Functional Class
- AE assessment
- 6MWT/Borg dyspnea score (6MWT to be initiated 3 to 6 hours after the last dose of UT-15C; Borg dyspnea score to be conducted immediately following 6MWT)
- Urine pregnancy test (for WOCBP)
- UT-15C dose titration
- Drug accountability/compliance
- Concomitant medications
- Weekly telephone calls are highly recommended, especially after any dose changes

7.1.3 Week 12 Visit

Subjects are to return to the study site at Week 12. This visit should be conducted within 14 days of the scheduled visit (as determined by the Baseline/Study Entry Visit) and the following assessments are to occur in the order recommended below:

- Vital signs (following at least 5 minutes of rest)
- WHO Functional Class
- AE assessment
- 6MWT/Borg dyspnea score (6MWT to be initiated 3 to 6 hours after the last dose of UT-15C; Borg dyspnea score to be conducted immediately following 6MWT)
- Urine pregnancy test (for WOCBP)
- Clinical laboratory assessments
- UT-15C dose titration
- Drug accountability/compliance
- Concomitant medications
- Monthly telephone calls are highly recommended

7.1.4 Follow-up Visits (every 12 weeks)

Subjects should return to the study site every 12 weeks after the Week 12 visit. These visits should be conducted within 14 days of the scheduled visit (as determined by the Baseline/Study Entry Visit). Assessment of AEs, concomitant medications, and dose titration should occur continuously between and during study visits. The recommended sequence of events for Follow-up Visits is displayed below:

- Vital signs (following at least 5 minutes of rest)
- WHO Functional Class
- AE assessment
- 6MWT/Borg dyspnea score (6MWT to be initiated 3 to 6 hours after the last dose of UT-15C; Borg dyspnea score to be conducted immediately following 6MWT)
- Urine pregnancy test (for WOCBP)
- Clinical laboratory assessments*
- Plasma NT-proBNP**
- UT-15C dose titration
- Drug accountability/compliance
- Concomitant medications
- Monthly telephone calls are highly recommended
- Collection of blood sample for evaluation of pharmacogenomics (optional) ***

**to be assessed at the first Follow-up Visit and every other visit thereafter*

***to be assessed at the third Follow-up Visit only (Week 48)*

**** The sample should be collected at the next scheduled Follow-up Visit when clinical labs are also collected. Subjects must sign an informed consent prior to sample collection.*

7.1.5 Study Termination Visit

When subjects discontinue the study, they will complete a Study Termination Visit. If possible, each subject should remain on study drug until they have completed the Study Termination visit. After the Study Termination Visit is completed, subjects should down titrate the study drug over an appropriate period of time in accordance with their clinical condition. Once the study drug has been discontinued, any remaining study drug should be returned to the clinic for drug accountability. The following assessments will take place at the Study Termination visit:

- Vital signs (following at least 5 minutes of rest)
- Physical examination
- WHO Functional Class
- AE assessment (for AEs ongoing at the Study Termination Visit, assessments to continue for up to 30 days beyond the Study Termination Visit)
- 6MWT/Borg dyspnea score (if possible, the 6MWT is to be initiated 3 to 6 hours after the last dose of UT-15C; Borg dyspnea score to be conducted immediately following 6MWT)
- Urine pregnancy test (for WOCBP)
- Clinical laboratory assessments
- Drug accountability/compliance
- Concomitant medications
- Collection of blood sample for evaluation of pharmacogenomics (optional) *

** If a subject discontinues prior to their next Follow-up Visit, pharmacogenomic samples will be collected at the Study Termination Visit.*

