3.2 OVERALL SCHEDULE OF TIMES AND EVENTS

Study Timeline	Baseline ^b (Study Entry)	Week 6 ^c	Week 12 ^c	Follow-up Visits (every 12 weeks) ^c	Study Termination Visit ^k
Informed consent	X				
Inclusion/exclusion criteria	X				
Vital signs ^a	X	X	X	X	X
Physical examination	X				X
6MWT / Borg dyspnea score ^d	X	X	X	X	X
WHO Functional Class	X	X	X	X	X
Clinical laboratory assessments	X		X	X ^e	X
Urine pregnancy test ^f	X	X	X	X	X
Dose titration	X	X	X	X	
NT-proBNP	X			X ^g	
Drug accountability/ Compliance	X	X	X	X	X
AEs	X ^h	X	X	X	X ⁱ
Concomitant medications	X	X	X	X	X
Phone calls ^j	X	X	X	X	X
Pharmacogenomic Sample (Optional)				X ^l	X ^l

Abbreviations: 6MWT, 6-Minute Walk Test; AE, adverse event; NT-proBNP, N-Terminal pro-brain natriuretic peptide; WHO, World Health Organization

^a Vital signs should be conducted following at least 5 minutes of rest and prior to or at least 30 minutes following the corresponding 6MWT.

^b Baseline/study entry assessments (6MWT/Borg dyspnea score, WHO Functional Class, clinical laboratory parameters, NT-proBNP, vitals, and physical examination) for this study are those collected at the Study Termination Visit from Study TDE-PH-310 and prior to initiation of open-label study drug. Informed consent and inclusion/exclusion criteria are exclusive to this Protocol.

^c Visit windows are ±14 days.

^d 6MWT must be conducted 3 to 6 hours after the last dose of UT-15C. Subject should rest for 5 minutes prior to each 6MWT.

^e During the follow-up visits, clinical laboratory samples should be collected at the first Follow-up Visit and every other Follow-up Visit thereafter.

^f If applicable, for women of child-bearing potential (WOCBP).

^g NT-proBNP should only be collected at the Follow-up Visit # 3 (Week 48).

^h Any AEs that are ongoing at the Study Termination Visit from Study TDE-PH-310 should be recorded as continuing AEs in this open-label study.

ⁱ Any AEs that are ongoing at the Study Termination Visit from Study TDE-PH-311 should be followed for up to 30 days after completion of the Study Termination Visit.

^j Phone calls to the subject should occur at least weekly for the first 12 weeks, and at least monthly thereafter.

^k After the Study Termination Visit is completed, subjects should down titrate the study drug over an appropriate period of time in accordance with their clinical condition. Once the study drug has been discontinued, any remaining supplies should be returned to the clinic for drug accountability.

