3.3.2.4 Adverse Event Assessments

Any AEs that are ongoing at the Study Termination Visit from Study TDE-PH-310 should be recorded as continuing AEs in this open-label study. Section 9 and Appendix 15.4 provide the guidelines and definitions for recording AEs.

All AEs will be captured from the time the informed consent form (ICF) is signed. All AEs should be followed until resolution (or return to normal or Baseline values), until they are judged by the Investigator to no longer be clinically significant, or for up to 30 days if the AE

extends beyond the final visit. All serious adverse events (SAEs) should be followed until resolution, death, or the subject is lost to follow-up even if they are ongoing more than 30 days after completion of the final visit. Sections 9 and Appendix 15.4 provide the guidelines and definitions for recording AEs.

Symptoms of PAH (disease-related events) should only be recorded as an AE if the event is either serious, new, or unusual with respect to intensity, frequency, duration as compared to symptoms in the subject's medical history, or there is a reasonable possibility that the event was caused by the study drug.

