3.6 ESTIMATED STUDY DURATION

The study will continue for approximately 6 years. The study may be discontinued at any time if, in the opinion of the Investigators and/or Sponsor, continuation of the study represents a serious medical risk to the subjects. This may include, but is not limited to, the presence of serious, life-threatening, or fatal AEs, or AEs that are unacceptable in nature severity, or frequency. The Sponsor reserves the right to discontinue the study for any reason at any time. Subjects that discontinue the study will be contacted approximately 30 days (± 5 days) after study drug discontinuation to confirm their survival status. Subjects may also continue to be

contacted after the final study visit to assess AEs/SAEs (see Section 9.2 for additional details).

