9.2 DOCUMENTATION OF ADVERSE EVENTS

All AEs will be captured from the time the ICF is signed. Any AEs that are ongoing at the Study Termination Visit from Study TDE-PH-310 should be recorded as continuing AEs in this open-label study. An AE or SAE occurring during the study must be documented in the subject's source documents and on the appropriate eCRF page. Information relating to the AE such as onset and cessation date and times, intensity, seriousness, relationship to study drug, and outcome is also to be documented in the eCRF (see Appendix 15.4 for definitions). Where possible, AEs should be recorded using standard medical terminology. If several signs

or symptoms are clearly related to a medically defined diagnosis or syndrome, the diagnosis or syndrome should be recorded on the eCRF page, not the individual signs and symptoms.

All AEs should be followed until either resolution (or return to normal or baseline values), until they are judged by the Investigator to no longer be clinically significant, or for up to 30 days, if the AE extends beyond the final visit. All SAEs that occur during the study will be followed until resolution, death, or the subject is lost to follow-up even if they are ongoing more than 30 days after completion of the final visit. Supplemental measurements and/or evaluations may be necessary to investigate fully the nature and/or causality of an AE or SAE. This may include additional laboratory tests, diagnostic procedures, or consultation with other healthcare professionals. The eCRF pages should be updated with any new or additional information as appropriate.

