11.3 DEATHS

All deaths will be listed (including those occurring within 30 days of the last UT-15C dose) by subject, and will include the subject number, treatment group in the parent study, date of assessment (day), whether subject died, date of death (day), and cause of death (including other, specify text [if applicable]). An additional listing of deaths will include the subject number, first UT-15C dose in TDE-PH-311 study, last UT-15C dose (day) in TDE-PH-311 study, date of death (day), and cause of death. The summary of deaths will be presented by the parent study and overall and will include the number (percent) of subjects who died (including those within 30 days of study participation) and their causes of death.

Time to death will be calculated as:

(the death date – the date of the first UT-15C dosing in TDE-PH-311 study)

The Kaplan-Meier (K-M) estimator will be provided for the time to death, and K-M plots will be provided by treatment group in the parent study.

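### New adverse events during the UT-15C taper and soon after the last dose are not systematically collected

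*Protocol*

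**What the plan says.** Protocol 7.1.5 keeps subjects on UT-15C, where possible, until the Study Termination Visit is done, and then: "After the Study Termination Visit is completed, subjects should down titrate the study drug over an appropriate period of time". Footnote k to the schedule in 3.2 says the same. Neither gives a duration.

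Four places set a 30-day AE rule:

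- 7.1.5: "for AEs ongoing at the Study Termination Visit, assessments to continue for up to 30 days beyond the Study Termination Visit".
- Footnote i in 3.2: "Any AEs that are ongoing at the Study Termination Visit from Study TDE-PH-311 should be followed for up to 30 days".
- 3.3.2.4: AEs are followed until they resolve, until they are "judged by the Investigator to no longer be clinically significant, or for up to 30 days if the AE" continues after the last visit.
- 9.2 repeats this: "or for up to 30 days, if the AE extends beyond the final visit".

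Section 3.6 requires a contact at about 30 days (±5) "after study drug discontinuation to confirm their survival status". It adds that subjects may also be "contacted after the final study visit to assess AEs/SAEs", which is a permission with no timing.

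The start of AE capture is fixed at consent (3.3.2.4, 9.2). Neither document gives an end date. SAP 11.3 does use a window tied to the last dose, but for deaths: "All deaths will be listed (including those occurring within 30 days of the last UT-15C dose) by subject". SAP 11.1 has no such window for AEs.

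**The concern.** Long-term safety is a secondary objective (Protocol 2.2). Under 7.1.5 the subject still takes the study drug, at falling doses, after the last scheduled AE assessment. The synopsis cautions that abrupt dose reductions can bring on poorly tolerated effects or a deterioration in PAH, and advises gradual titration. The taper follows that advice. It is still the period in which withdrawal effects would appear, and the time just after the last dose belongs with it.

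The documents count from the end of treatment for the survival contact (3.6), for contraception in women (4.1) and for deaths (SAP 11.3). New AEs are the exception. What is at stake is whether the record of the withdrawal period can be compared across sites, or depends on how much each site chooses to ask. There is also a smaller effect on the events per patient-year in SAP 11.1, if taper days count as exposure while taper events are incompletely collected.

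**Working it through.** **1. Trace one event through the text.** Suppose a subject attends the Study Termination Visit on drug, starts the taper, and has a new non-serious AE ten days later.

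- 7.1.5 and footnote i: the AE was not ongoing at the visit, so it is not covered. Both clocks run from the visit, not the last dose.
- 3.3.2.4 and 9.2, 30-day rule: an AE that began after the final visit does not extend beyond it, so it is not covered.
- 9.2, capture from consent: nothing excludes the AE, but no end date is given. Section 7.1.1 asks for continuous reporting while the study lasts. Section 7.1.5 has the visit done when the subject leaves the study, so it is unclear whether the taper counts.
- 6.1: dose changes should involve the site, a subject who changes dose unprompted should call, and AE calls are at least monthly after Week 12. The schedule ticks calls in the Study Termination column, but the 7.1.5 list omits them.
- 3.6: the required contact confirms survival, and AE contact is optional.
- Drug return (7.1.5, footnote k): no date and no AE question.
- 9.1.1: AEs may include post-treatment events caused by protocol-mandated procedures. This arguably reaches taper effects but sets no collection period.
- 9.3: not applicable to this event. A serious one must be reported within 24 hours of the site learning of it, with no end date.

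The AE may be recorded, but no clearly required step asks about it.

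**2. Can 30 days from the visit end before the drug does?** The documents give no taper length, so this needs an assumption: the general reduction steps in 6.1 (0.125 or 0.25 mg, every 12 to 24 hours) apply to each of the three daily doses.

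Taper days = (dose ÷ step) × interval in days.

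- 12 mg TID (lower bound of the SAP's top dose category, SAP 9.3.5): fastest 12 ÷ 0.25 × 0.5 = 24 days; slowest 12 ÷ 0.125 × 1 = 96 days.
- Dose at which the taper takes exactly 30 days: slowest 30 × 0.125 = 3.75 mg TID; fastest 30 ÷ 0.5 × 0.25 = 15 mg TID.
- TDE-PH-304 mean doses of 3.9 to 5.9 mg BID (Protocol 1.2.4), converted by daily total: 3.9 × 2 ÷ 3 = 2.6 and 5.9 × 2 ÷ 3 = 3.93 mg TID. Shortest taper 2.6 ÷ 0.25 × 0.5 = 5.2 days; longest 3.93 ÷ 0.125 × 1 = 31.5 days.

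So at those mean doses the taper mostly fits inside 30 days. At higher doses it may not, and 6.1 sets no maximum dose.

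**3. Scale.** The mean exposure reported for TDE-PH-304 is 138.8 weeks. Against that, 5.2 to 31.5 days is 5.2 ÷ 7 = 0.7 to 31.5 ÷ 7 = 4.5 weeks. This compares time only and says nothing about AE rates in the taper, which the documents do not give.

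**4. Analysis side.** SAP 11.1 has an earliest onset date and no latest one, so any AE that is recorded is analysed. The loss is in collection. SAP 9.1 lists first and last dose dates and exposure in weeks, but does not state how exposure is counted.

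**5. Visit timing.** Protocol 8.1 asks for every effort to do the termination evaluations after treatment has ended; 7.1.5 has the visit on drug where possible. A site following 8.1 would cover the taper at the visit. A site following 7.1.5 would not.

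**The case against.** The best defence is that the 30-day text says how long to follow an AE, not when to stop recording new ones. Capture under 9.2 is open-ended and nothing tells a site to close the AE record at the visit. That stands. A reader might infer that new AEs after the visit are excluded by rule; the documents do not say so.

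A taper is also a series of dose changes, and 6.1 calls for site consultation on each. If monthly calls continue, a taper of a month or more would contain one. This narrows the gap. It does not close it, because calls after the visit are not clearly required, short tapers can fall between them, and none is tied to the period after the last dose.

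A reader might infer that SAEs or deaths are lost. The open-ended duty in 9.3 and the survival contact in 3.6 argue against that. What remains is an SAE of which the site never hears.

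Section 9.1.3 also matters. Non-serious events on the Appendix 15.5 list that the investigator attributes to PAH progression are kept out of AE recording, unless possibly drug-caused or worse than expected. Some worsening PAH in the taper is therefore not an AE by design, and a fix limited to AEs would miss it.

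Finally, the primary objective is drug provision and the analysis is descriptive (Protocol 2.1, 10.3). That limits the consequence but does not remove the safety objective.

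**Conclusion.** The point holds as unsystematic ascertainment of new, mainly non-serious AEs during the taper and soon after the last dose. It is worth correcting because a safety objective is affected and the remedy uses a contact already in the plan. It does not threaten the study.

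Its size cannot be worked out from the documents. A reader might be tempted to turn taper length into a percentage shortfall in the AE rate. That would need a taper AE rate, the share of subjects who taper, the share of events missed and an exposure definition, and none of these is given. Against multi-year exposure the effect on overall rates is probably small.

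The claim that a visit-anchored 30 days can end while the subject is still on drug rests on applying the 6.1 steps to the taper. Subjects who move straight to commercial drug may not taper at all.

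**What to change.** **Protocol, main change.** In 3.3.2.4, 7.1.5, 9.2 and footnote i, require new AEs and SAEs, and disease-related events under 9.1.3, to be recorded through 30 days after the last study-supplied UT-15C dose. Run the 30-day follow-up of ongoing AEs from that dose too. In 3.6, have the existing 30 (±5) day contact ask about AEs and SAEs as well as survival. Leave the SAE duty in 9.3 open-ended.

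**Secondary.** Align 8.1 with 7.1.5: visit on drug before the taper where possible, otherwise as soon as possible after the drug stops. In the SAP, count exposure from first to last dose including the taper, so that the numerator and denominator of the AE rates cover the same time. Flag AEs by onset relative to the last dose, without excluding later recorded events.

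**Cost.** Wording in about six protocol places, one more question at a contact already planned, and one exposure definition and one flag in the SAP. No new visit is needed. Data entry rises slightly, and some added AEs may reflect whatever therapy replaces UT-15C; the onset flag helps to separate them.
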